### 3.1 Sample Management

- **Molecular analyses** will be performed using state-of-the-art technologies, in particular next-generation sequencing (NGS) of both second- and third-generation (short-read [SR] and long-read [LR]) platforms for DNA and/or RNA sequencing at the Genoa and Aosta (CMP3VdA) sites of the Istituto Italiano di Tecnologia Foundation.
- **NGS analyses of single genes, gene panels, clinical exome, and/or whole exome (WES)**—when indicated in the clinical management of these patients—will be carried out at the laboratories of IRCCS Policlinico San Martino (Genoa) and Fondazione IRCCS Policlinico Cà Granda (Milan). When necessary, these may also be performed at the IIT sites in Genoa and Aosta (CMP3VdA).
- **Proteomics, metabolomics, and lipidomics analyses:** Laboratory selection is ongoing to identify centers able to perform these investigations in accordance with the quality standards imposed by the project. Once identified, relevant ethical committees will be notified.
- **Data management and privacy:** The study's principal investigator is responsible for ensuring participant privacy. Study data will be recorded in a validated Data Management System via an electronic Case Report Form (eCRF), provided by the Scientific Directorate of IRCCS Policlinico San Martino (Genoa) and Fondazione IRCCS Policlinico Cà Granda (Milan). The REDCap (Research Electronic Data Capture) platform will be employed. The REDCap consortium comprises >1,000 institutional partners worldwide and supports secure web-based applications for research data collection. REDCap enables rapid and secure creation/management of online databases and is currently used for >110,000 projects with ~150,000 users across multiple research fields.  
For this study, REDCap will enable:
  - a) user-level identification with role-based access restrictions;
  - b) real-time data integrity validation;
  - c) patient de-identification prior to data export;
  - d) centralized data storage with daily backup on secure servers within the IT infrastructure of IRCCS Policlinico San Martino and Fondazione IRCCS Policlinico Cà Granda.
- **Biobanking:** Within the NeurOmics project, the Biological Resource Center (CRB) of IRCCS Policlinico San Martino and the Telethon Biobank of Fondazione IRCCS Policlinico Cà Granda will coordinate the collection, processing, and short- and long-term storage of samples, as well as their redistribution.

Specifically, the CRB will:

1. Develop the workflow for biological material management at the Genoa center and harmonize all study SOPs in collaboration with the Telethon Biobank (Milan).
2. Prepare blood collection kits to trace pre-analytical variables such as vacutainer batch number, order of tube collection, fill volume, and time between sampling and processing. Each kit, assigned at enrollment, will contain:
  - a) a CRF for pre-analytical and storage data (completed by phlebotomist/nurse and CRB staff);
  - b) a 5 mL vacutainer with clot activator and gel separator for serum (Ref: Vacuette®, Greiner 456073);
  - c) a 6 mL K3EDTA vacutainer for plasma (Ref: Vacuette®, Greiner 456036);
  - d) a 9 mL K3EDTA vacutainer (Ref: Vacuette®, Greiner 455036) for PBMC isolation using Ficoll.
3. Ensure sample quality (high-quality samples) through dedicated internal and/or external quality controls.

4. Trace all pre-analytical, analytical, and storage-related information via biobank software. These data will be pseudonymized and linked to laboratory, clinical, and follow-up data (well-annotated data).

#### 4. STUDY DURATION

The study will have an overall duration of **10 years**. Follow-up assessments will be conducted periodically, as per routine clinical practice for each condition under investigation.

#### 5. STUDY OBJECTIVES

The study aims to collect omics characterization for at least **1,000 patients** with neurodegenerative diseases, recruited from the Neurology and Geriatrics Units of IRCCS Policlinico San Martino (Genoa), Fondazione IRCCS Policlinico Cà Granda (Milan), and other units joining after ethics committee approval. Estimated recruitment: >400 dementia/cognitive impairment cases, >450 PD/parkinsonism cases, ~150 ALS/motor neuron disease cases. The primary goal is to identify, through whole-genome analysis, both rare and common monogenic and polygenic variants—single nucleotide variants (SNVs) and structural variants (CNVs, insertions, translocations, inversions, mobile element insertions [MEIs])—that may be causative or confer increased risk for neurodegenerative diseases. Integration with other omics sciences will enable correlation of these variants with gene, protein, and metabolic expression patterns, thereby defining distinct molecular trajectories underlying neurodegeneration and their impact on disease progression.

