### 3. STUDY DESIGN

**NeurOmics** is a multicenter, prospective, observational study enrolling patients diagnosed with neurodegenerative diseases, including Parkinson’s disease and degenerative parkinsonisms, neurodegenerative cognitive disorders at the stage of mild cognitive impairment (MCI) or early/late-onset dementia, and motor neuron diseases (ALS). The study aims to identify pathogenic genomic variants and/or dysregulated molecular pathways in these patients by performing whole-genome sequencing and integrating these data with transcriptomic, epigenomic, and/or proteomic profiles. It further aims to identify novel biomarkers for the diagnosis and monitoring of neurodegenerative diseases through the analysis of biological samples (e.g., blood and derivatives), including liquid biopsy approaches using the most advanced technologies currently available.

The study plans to enroll at least **1,000 individuals** with neurodegenerative disease (see section *7.4 Statistical Analysis*).

Thanks to the availability of large public databases containing whole-genome sequences from healthy populations, such as **gnomAD** and the **1000 Genomes Project**, these datasets can be used as controls for variant identification in participants diagnosed with PD and parkinsonisms, early- and late-onset dementias (including MCI), and ALS. For example, the 1000 Genomes Project provides a catalog of common human genetic variants derived from self-reported healthy individuals, which has become a widely used reference in biomedical genomics.

To confirm the association of variants identified in this study with the relevant neurodegenerative disease, their presence will be checked against curated mutation repositories, including **ALZFORUM** and the **Alzheimer’s Disease Neuroimaging Initiative (ADNI)** (<http://adni.loni.usc.edu/>) for AD, and **PPMI** for PD. For subjects with MCI, genomic data deposited in ADNI (including controls, AD cases, and MCI) will be used. For ALS, the study will leverage the **Project MinE** database and genomic resources.

The case series and available data from each reference database are summarized in **Table 1**, while detailed statistical methodology is provided in section *7.4 Statistical Analysis*.

Database Name	Type of Sequencing	Number of Genomes (WGS), Exomes (WES), Genes, SNPs, Indels, SVs or CNV	Number of Subjects	Type of Case

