## 7.4 Statistical Analysis

### Sample Size

Given the nature of this study, sample size is not determined by a formal statistical power calculation but rather by projections of i) the number of patients with neurodegenerative diseases expected to be referred to the two experimental centers during the 10-year project period, and ii) an estimated compliance rate of approximately 80%.

We anticipate enrolling at least 1,000 patients with neurodegenerative diseases, distributed approximately as follows:

- a) Parkinson's disease (PD): ~30% of cases
- b) Parkinsonism: ~5% of cases
- c) Dementias:
  - Alzheimer's disease (AD): ~30% of cases
  - Frontotemporal dementia (FTD): ~10% of cases
  - Young Onset Dementia (YOD): ~5% of cases
  - Mild Cognitive Impairment (MCI): ~5% of cases
- d) Amyotrophic lateral sclerosis (ALS): ~15% of cases.

Additionally, ~200 geriatric controls with negative neurological evaluation and negative family history of neurodegeneration will be enrolled as internal controls.

The projected cohort of ~1,000 patients is based on the epidemiology of neurodegenerative diseases observed at IRCCS Policlinico San Martino (Genoa) and Fondazione IRCCS Policlinico Ca' Granda (Milan). The expected distribution across disease categories should allow reliable characterization of clinical and molecular subgroups.

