### Statistical Approaches

Descriptive statistics will be generated to report the percentage of variants relative to the total enrolled cohort and to the control populations (European and Italian), stratified by disease (PD, parkinsonism, AD, FTD, YOD, ALS, and MCI), individual genes, and specific mutations.

Molecular–genetic data (single variants or variant groups) and clinicopathological data (diagnosis, disease stage, prognostic/predictive parameters, survival) will be analyzed using both numerical and graphical approaches. Frequency and contingency tables will be constructed, and statistical indices (means, percentiles, standard deviation) will be computed. Data will be visualized through histograms, boxplots, and scatterplots. Appropriate statistical tests—including t-tests, Fisher's exact test, and others depending on the formulated hypotheses—will be applied. Enrolled patients will be monitored through active follow-up as part of routine diagnostic care. Data regarding disability progression, disease course, and overall survival will be analyzed by diagnosis, mutation, or mutation combinations, as well as treatment received, using Kaplan–Meier survival analysis.

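### Parkinsonism is a planned and reported group with no criteria set in Section 6, and Section 5's more than 450 PD/parkinsonism cases do not match the roughly 350 implied by Section 7.4

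*Protocol*

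**What the plan says.** **Population and reporting.** Section 3 (Study Design) describes the enrolled diseases as PD together with "degenerative parkinsonisms, neurodegenerative cognitive disorders at the stage of mild cognitive impairment (MCI") or dementia, and ALS. Section 7.4 (Sample Size) lists "Parkinsonism: ~5% of cases" on its own line, apart from PD and apart from the dementias. Section 7.4 (Statistical Approaches) plans descriptive results "stratified by disease (PD, parkinsonism, AD, FTD, YOD, ALS, and MCI").

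**Eligibility.** Section 6 says that the diagnosis follows the criteria it goes on to list, and that only subjects meeting all inclusion criteria and no exclusion criterion for the condition are enrolled. Six sets follow: AD, FTLD, DLB, MCI, ALS and PD. The PD set requires a clinical diagnosis of PD under the revised MDS criteria, and failing any inclusion criterion is itself an exclusion.

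**Recruitment.** Section 5 estimates ">400 dementia/cognitive impairment cases, >450 PD/parkinsonism cases, ~150 ALS/motor neuron disease cases" from the Genoa and Milan units "and other units joining after ethics committee approval". Section 7.4 starts from the patients "expected to be referred to the two experimental centers during the 10-year project period" and gives percentage shares, among them "Amyotrophic lateral sclerosis (ALS): ~15% of cases". It adds: "The projected cohort of ~1,000 patients is based on the epidemiology of neurodegenerative diseases" seen at the Genoa and Milan hospitals.

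**The concern.** Eligibility is a matter for the protocol, and Section 6 is written as a closed rule. A group that is planned and reported but has no criteria set cannot be filled by following that rule, so the parkinsonism stratum in the results would be largely empty. The protocol also carries two planned sizes for the combined PD/parkinsonism group. The study has no formal power calculation, so no error rate or power figure changes. What is at stake there is a single, usable statement of what the study intends to recruit.

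**Working it through.** **1. Entry route for non-PD parkinsonism**

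| Section 6 set | What it requires | Entry as parkinsonism? |
|---|---|---|
| PD | Clinical diagnosis of PD, revised MDS criteria | No |
| FTLD | Behavioural/dysexecutive or language presentation, with matching imaging | No, only as FTLD |
| DLB | Predominantly non-amnestic cognitive impairment, with supportive findings | No, only as DLB |
| MCI | Memory complaint and objective memory deficit | No, only as MCI |
| AD | Predominantly amnestic presentation, with AD biomarkers | No |
| ALS | Definite or probable ALS, with EMG findings | No |

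Planned size of the group: 0.05 × 1,000 = 50.

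The same comparison for the other groups in Section 7.4: young-onset dementia (YOD, about 5%) and the approximately 200 geriatric controls also have no set of their own in Section 6. In the other direction, DLB has a set but no share in Section 7.4 and is not named among the reporting strata.

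**2. Recruitment figures**

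Inputs from Section 7.4: PD 30%, parkinsonism 5%, AD 30%, FTD 10%, YOD 5%, MCI 5%, ALS 15%. Sum: 30 + 5 + 30 + 10 + 5 + 5 + 15 = 100%. Projected cohort: about 1,000.

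| Group | Section 7.4 share × 1,000 | Section 5 | Agreement |
|---|---|---|---|
| PD/parkinsonism | (30% + 5%) × 1,000 = 350 | more than 450 | No |
| Dementia/MCI | (30% + 10% + 5% + 5%) × 1,000 = 500 | more than 400 | Yes, bound met |
| ALS | 15% × 1,000 = 150 | about 150 | Yes |

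Gap in the first row: 450 − 350 = 100, and 100/350 = 29%.

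**3. Can the PD/parkinsonism figures be reconciled?**

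- Printed shares, larger total: 450/0.35 = 1,286. ALS would then be 0.15 × 1,286 = 193, against about 150.
- Adding the 200 controls to the denominator: 0.35 × 1,200 = 420, still below 450.
- Each share off by up to 2.5 points (assumption): PD/parkinsonism is at most 32.5% + 7.5% = 40%. At 1,000 that is 400, still below 450. Reaching 450 needs 450/0.40 = 1,125.
- Same rounding with ALS held at 150: ALS is at least 12.5%, so the total is at most 150/0.125 = 1,200. At 1,125 the split is 40.0% PD/parkinsonism, 13.3% ALS and 46.7% dementia/MCI. At 1,200 it is 37.5%, 12.5% and 50.0%.

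**The case against.** **The total is not fixed at 1,000.** The protocol says at least 1,000 in Sections 3, 5 and 7.4, the shares are approximate, and Section 5 counts units that may join while Section 7.4 projects from two centers. If the ALS figure is also allowed 10% tolerance (165 cases, an assumption), then with the same 2.5-point rounding the total can reach 165/0.125 = 1,320. At 1,286, for example, 450 PD/parkinsonism, 165 ALS (12.8%) and 671 dementia/MCI (52.2%) fit together. This stands: it would be wrong to say that no total reconciles the two sections. But Section 7.4 ties its distribution to a projected cohort of about 1,000, where rounding alone does not reach 450. No larger total is stated, and nothing says that joining units make up the difference.

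**The missing set may be a labelling mismatch with DLB.** The DLB set accepts reduced striatal dopamine transporter uptake as supportive evidence, so some parkinsonism cases might be meant to enter there. The documents do not confirm this. Section 7.4 lists parkinsonism apart from the dementias, and the DLB set requires cognitive impairment.

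**Sample destruction.** A reader might infer from Section 8 (Screening Failure) that parkinsonism patients would routinely have their data deleted and samples destroyed. Section 7.1 has the investigator check the criteria before inviting the patient, so such a patient would normally not be invited. Section 8 applies only where ineligibility is found after consent.

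**A second conflict in the dementia row.** A reader might set 40/45/15% (Section 5) against 50/35/15% (Section 7.4). That treats the lower bounds of more than 400 and more than 450 as shares. The documents give no such distribution in Section 5.

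**Conclusion.** Both parts hold. First, Section 6 gives no route by which non-PD parkinsonism can be enrolled as such, although it is a planned group of about 50 in 1,000 and a separate reporting stratum. The consequence is non-enrolment of that group. The number affected is at most about 50, because some patients may meet the FTLD, DLB or MCI set and enter under that diagnosis; the documents do not allow that number to be estimated.

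Second, PD/parkinsonism has two planned sizes, about 350 and more than 450. They differ by at least 100 at the projected total of about 1,000 and fit only at a larger, unstated one. The threshold of about 1,125 rests on the assumed 2.5-point rounding of each share. This part is a reconciliation of the text with no effect on power. The missing criteria set is the more important of the two, because it decides who may enter. The uncounted DLB group is minor.

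**What to change.** 1. Reconcile Section 6 with Sections 3 and 7.4 so that every planned and reported group has a stated entry route. This covers parkinsonism, and also YOD and the approximately 200 controls. The content of the criteria is for the sponsor to decide.
2. State one total and one distribution in Sections 5 and 7.4. If Section 7.4 is intended, that is about 350 PD/parkinsonism, 500 dementia/MCI and 150 ALS. If Section 5 is intended, restate the total and shares to match, and say whether joining units supply the difference.
3. Say in which group DLB is counted in the Section 7.4 shares and reporting strata.

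The cost is a text amendment to Sections 5, 6 and 7.4, notified to the Ethics Committee as Section 9 requires. Keeping Section 7.4 lowers the stated PD/parkinsonism figure from more than 450 to about 350. Keeping Section 5 means either a total above 1,000 or, at 1,000, a dementia/MCI group of no more than about 1,000 − 450 − 150 = 400 instead of 500.

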##### Primary Objectives

1. Identify genomic variants not yet recognized as causes or susceptibility factors for neurodegenerative diseases, through WGS and dedicated bioinformatic pipelines (including protein-coding genes, noncoding RNA genes, regulatory DNA sequences—promoters, enhancers, repeats—and both SNVs and SVs).
2. Assess correlations between genetic–molecular alterations and clinical phenotype (e.g., severity, comorbidities) for the most frequent variants.
3. Identify splicing variants associated with neurodegenerative diseases using genomic and transcriptomic analyses.
4. Detect SNVs and/or SVs affecting enhancer or promoter regions.
5. Identify molecular mechanisms associated with neurodegenerative diseases and their impact on disease progression via multi-omics approaches.
6. Identify novel diagnostic, prognostic, and predictive biomarkers in neurodegenerative diseases.

##### Secondary Objectives

1. Identify causative or susceptibility genomic variants and provide accurate genetic counseling to patients and families.
2. Investigate associations between pathogenic variants in neurodegeneration-related genes and systemic comorbidities to inform prevention and early treatment.
3. Identify and characterize molecular markers (genes, transcripts, proteins, pathways) commonly dysregulated across different neurodegenerative diseases (e.g., cross-disorder gene overlap).
4. Identify cross-talk between known causative/susceptibility variants and additional transcripts/proteins/pathways influencing penetrance/expressivity of neurodegenerative disorders.

This study lays the foundation for defining homogeneous patient subgroups with combined clinical and genomic features, ultimately enabling personalized therapeutic strategies.

Given the sample size, disease-specific targeted studies may be conducted on selected subgroups. For example in Parkinson's disease, transcriptomic analyses will be performed in early-onset PD cases to detect expression or splicing defects in known PD genes, thereby revealing candidate genes with cryptic pathogenic variants through genome–transcriptome integration. Genetic data from PD patients will also be used to investigate associations between excess rare variants in predefined gene clusters (e.g., protein misfolding, mitochondrial dysfunction/oxidative stress, endolysosomal defects) and clinical phenotype, stratifying patients by progression rate: rapid progression (Hoehn & Yahr  $\geq 2.5$  at 5 years) versus slow progression (Hoehn & Yahr  $\leq 1$  at 5 years).

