**PARKINSON'S DISEASE (PD)**

**Inclusion criteria**

- Signed written informed consent from the patient and/or legal representative (Appendix X);
- Age  $\geq 18$  years;
- Clinical diagnosis of PD according to revised MDS criteria, as follows:

- Predominant motor presentation with bradykinesia plus resting tremor and/or rigidity;
- MMSE  $>24$ , with preserved (MCI) or mildly impaired (mild dementia) instrumental daily living activities (CDR 0.5–1);
- Absence of significant neurological/systemic comorbidities or structural abnormalities indicative of other causes of cognitive impairment;
- Imaging findings:
  - a) Normal structural brain imaging;
  - b) Striatal DAT binding reduction on SPECT DAT-SCAN;
- Availability of longitudinal clinical assessments, including motor scales (e.g., UPDRS-III, Hoehn & Yahr), MMSE/MOCA, and daily living activities, for at least 24 months.

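### Does the Parkinson's disease example wrongly leave out patients at Hoehn & Yahr 1.5 to 2 when it contrasts rapid with slow progression?

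*Protocol*

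**What the plan says.** The contrast stands at the end of Secondary Objectives, after the four numbered items. It is introduced by the statement that "disease-specific targeted studies may be conducted on selected subgroups", and Parkinson's disease serves as the example. Within that example, "Genetic data from PD patients will also be used to investigate associations between excess rare variants in predefined gene clusters" and the clinical phenotype, "stratifying patients by progression rate: rapid progression" (Hoehn & Yahr at least 2.5 at 5 years) against slow progression (at most 1 at 5 years). No other stratum is named.

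Four other places bear on the point:

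- **Sequencing.** Section 3 describes finding variants and dysregulated pathways "in these patients by performing whole-genome sequencing and integrating these data" with other omics profiles. Section 5 says "The primary goal is to identify, through whole-genome analysis", variants that cause disease or raise its risk. Neither limits sequencing to phenotypic extremes.
- **Assessments.** The Parkinson's disease inclusion criteria ask for "Availability of longitudinal clinical assessments, including motor scales (e.g., UPDRS-III, Hoehn & Yahr), MMSE/MOCA, and daily living activities, for at least 24 months".
- **Follow-up.** Section 4: "Follow-up assessments will be conducted periodically, as per routine clinical practice for each condition under investigation".
- **Other progression analyses.** Section 7.4, Statistical Approaches: "Data regarding disability progression, disease course, and overall survival will be analyzed by diagnosis, mutation, or mutation combinations".

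**The concern.** The 2.5 cut-off implies a scale with half steps, so the two cut-points leave stages 1.5 and 2 unassigned. Extreme-group designs are usually chosen to save sequencing or phenotyping, and neither is saved here. The genomes are planned for the whole cohort, and a 5-year stage must be known before anyone can be placed inside or outside the strata. A reader may therefore suspect that patients who cost nothing extra are discarded, and that power suffers badly if few patients remain at stage 1 or below after 5 years. At stake would be a missed association between gene-cluster burden and progression.

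**Working it through.** **Is there a planned figure to miss?** No. Section 7.4 says that the sample size does not come from a power calculation. The protocol gives no power, effect size or expected 5-year stage distribution for this contrast. Any loss must be judged on assumed inputs.

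**Inputs.** Section 7.4 puts Parkinson's disease at about 30% of at least 1,000 patients: 0.30 × 1,000 = 300. Assumed: all 300 have a 5-year stage, two-sided α = 0.05, and the stage shares and effect shapes below.

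**Analytic check, linear effect on a latent normal progression trait.** Let s, m and r be the slow, middle and rapid shares, and μ_s, μ_m, μ_r the latent means in those groups.

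- Information of the extreme contrast, relative to the full continuous trait: E = s·r/(s+r) × (μ_r − μ_s)².
- Information of a three-level ordered analysis with scores 0, 1, 2: L = (m·μ_m + 2r·μ_r)² / (m + 4r − (m + 2r)²).
- Power of the extreme contrast when the three-level analysis has 80%: Φ[(1.960 + 0.842)·√(E/L) − 1.960].

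Unbalanced tails, s = 0.05, r = 0.25: μ_s = −2.06, μ_r = 1.27, E = 0.463, L = 0.681, E/L = 0.68. Power is Φ(2.802 × 0.825 − 1.960) = Φ(0.35) = 64%, a loss of 16 points.

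Balanced tails, s = r = 0.20: μ_s = −1.40, μ_r = 1.40, E = L = 0.784. Power is 80%, no loss.

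So even under a linear effect, the loss against a three-level analysis runs from 0 to 16 points over the shares examined. Against a full continuous measure at 80% power, the extreme contrast has about 48% to 71%.

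**Simulation, other effect shapes.** N = 300, 15% carriers (assumed), 100,000 replicates per layout. Shares are slow/middle/rapid in %. An arrow goes from non-carriers to carriers. Power is in %.

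| Assumed effect | Shares | Extremes | Ordinal, all | Three-group (2 df), all |
|---|---|---|---|---|
| Uniform 0.45 SD shift | 5/65/30 | 21 | 64 | 50 |
| | 10/50/40 | 41 | 66 | 52 |
| | 15/45/40 | 53 | 66 | 53 |
| | 25/50/25 | 69 | 70 | 59 |
| | 30/40/30 | 69 | 69 | 59 |
| Carriers mainly lose the benign course | 15/45/40 → 3/45/52 | 74 | 54 | 57 |
| | 20/40/40 → 5/40/55 | 83 | 70 | 70 |
| | 20/40/40 → 5/50/45 | 67 | 30 | 64 |
| | 25/50/25 → 8/67/25 | 47 | 29 | 70 |
| Carriers move only from middle to rapid | 10/50/40 → 10/28/62 | 10 | 65 | 74 |
| | 15/45/40 → 15/23/62 | 14 | 59 | 77 |
| | 5/65/30 → 5/45/50 | 6 | 66 | 65 |
| | 25/50/25 → 25/30/45 | 30 | 42 | 75 |

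Ordinal minus extremes, before rounding: 0 to +43 points in the first block, −12 to −36 in the second, +12 to +59 in the third. At N = 150 the ranges are +1 to +35, −4 to −16 and +9 to +38.

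The three-group test does not dominate either. In the second block it falls from 74 to 57 and from 83 to 70 against the extremes. Under a uniform shift with balanced tails it falls from 69 to 59.

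**What the calculation shows.** The direction of the gain depends on how the genes act on progression, which is what the sub-study would investigate. In the third block the slow share is the same in carriers and non-carriers, so a contrast anchored on the slow group is bound to do poorly there. Rejection under the null was 4.0% to 5.1% for all three tests, so type I error does not separate them.

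**The case for a change.** The strongest opposing case has three parts. First, the cut-points are fixed numerically and incompletely. The text speaks of stratifying patients and says the genetic data will be used this way, so it is not explicit that the middle is meant to be excluded. Second, the contrast is fragile: its lowest power over the 13 layouts is 6%, against 29% for the ordinal test and 50% for the three-group test. Third, changing it would need only wording.

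Part of this stands. The gap at stages 1.5 and 2 is real, no sequencing is saved, and in some settings an all-patient analysis would be much stronger. But selecting extremes fits an introduction that speaks of selected subgroups, and cleaner phenotypes are a legitimate reason for it. The lowest-power comparison depends on which layouts are included. Moving to an ordinal analysis adds a proportional-odds assumption and loses power where carriers mainly lose the benign course.

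The undefined origin of the 5 years, the 24-month assessment requirement and the routine follow-up limit any analysis of a 5-year stage equally. They do not count against this contrast in particular.

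**Conclusion.** The concern does not hold. The protocol offers a valid, unbiased extreme-group contrast as an example of optional targeted work, and it contradicts no power or size stated for it. Replacing it would be a trade-off, from −36 to +59 power points for the ordinal analysis at N = 300. That range rests on assumed carrier share, stage distribution, effect shape and number of patients with a 5-year stage. It also treats burden as carrier or non-carrier, although an excess of rare variants could be a count. Patients at stages 1.5 and 2 are not lost: Section 7.4 analyses progression and disease course by mutation and mutation combination without these cut-points, and Primary Objectives 2 and 5 cover severity and progression. The handling of the middle stages, the origin of the 5 years and the choice of test for an unnumbered example are commonly settled in a statistical analysis plan, which was not available here. What remains is a preference between defensible analyses.
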